- Maximum blood pressure reading of 166/100 mmHg
- Vital pulp (Cold and EPT positive)

Exclusion Criteria:

- History of inadequately controlled hypertension or active thyroid disease
- Five or more nosebleeds in the past month
- Known allergy to oxymetazoline, tetracaine, benzylalcohol or para-aminobenzoic acid
- History of congenital or idiopathic methemoglobinemia
- Taking monoamine oxidase inhibitors, tricyclic antidepressants (e.g. amitriptyline), or non-selective beta adrenergic antagonists (e.g. propranolol)
- Taking oxymetazoline-containing products (i.e., Afrin) in the last 24 hours

- Pregnant and lactating women
- Non vital pulp (Cold and EPT negative)

Study Characteristics:

Design:

Randomized, open label clinical trial

Non-inferiority threshold and Sample size calculation:

The anesthetic efficiency of articaine has been reported in the literature to be around 78 – 88% (Evans et al.). The non-inferiority threshold is the maximum allowable excess of outcome events arising from the novel treatment compared with the standard treatment. The threshold for this study has been selected based on draft guidance set by the FDA (Temple et al.) and was set at 25%. Using nQuery Advisor v7.0, we verified that a sample size of 38 subjects per group would be needed to show a non-inferiority of <25% (one sided alpha of 0.05 and a power of 83%).

Accordingly, each of our study arms will have 90 subjects: 45 in Kovanaze and 45 in Articaine groups.

Accounting for screen failures and dropouts, we will recruit 100 participants in each population totaling 300 for the entire study.

Intervention:

Metered Kovanaze sprays (0.2 ml each spray, St. Renatus) in the nostril on the same side as the tooth of interest. The dose involves:

2 sprays in adult and kids weighing 40 kg or more

1 spray in kids > 6 years but weighing between > 20 kg and < 40 kg

Control:

- Children: 1.0 ml of 4% articaine (containing 1:100000 epinephrine) delivered in the periapex of the tooth of interest by labial/buccal infiltration
- Adults: 1.8ml of 4% articaine (containing 1:100000 epinephrine) delivered in the periapex of the tooth of interest by labial/buccal infiltration

Population:

Our study will evaluate the effectiveness of Kovanaze in three different populations.

Population 1: *Children (aged 6-17 years and weighing >20 kg) requiring specific procedures for treatment of oral disease*

Location: Department of Pediatric Dentistry, 3rd floor, Wood Building

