- b. Mild pain was defined as greater than 0 mm and less than or equal to 54 mm. Mild pain included the descriptors of faint, weak, and mild pain.
- c. Moderate pain was defined as greater than 54 mm and less than 114 mm.
- d. Severe pain was defined as equal to or greater than 114 mm. Severe pain included the descriptors of strong, intense, and maximum possible.

If study participants experience pain/ sensitivity/ discomfort at any time during the procedure (VAS >54), the local anesthesia would be considered a failure and rescue anesthetic (0.7 ml of articaine deposited at the periapex of the tooth of interest) administered to complete the intended procedure.

Secondary Outcome Measures in Adults:

- 1. Onset of meaningful anesthesia:** Patient will be given a stopwatch and will be instructed to press the watch at two different time points:
 - a. Onset of anesthesia (T-1 in min): Press the watch when they first perceive pain relief after the administration of local anesthetic
 - b. Significant pain relief (T-2 in min): Press the watch the second time when the patient report significant pain relief (<54 in VAS scale)

At each time of the stopwatch/ timer, the patient will record their pain in VAS scale. Treatment will proceed as long as the VAS rating is below 54mm. i.e. no to mild pain. If the pain is moderate to high at any point of the procedure (score of 54 or higher), the event would be considered anesthetic failure and a rescue anesthetic administered.

2. Spread of anesthesia:

The teeth and the soft tissues on the side of the mouth ipsilateral to the tooth of interest will be evaluated for spread of anesthesia. The number of teeth that are anesthetized will be counted after cold and electronic pulp tests and recorded (maximum possible score is 5). Similarly, the buccal and lingual gingiva will be tested for anesthesia 1 cm below the gingival margin for each of the 5 teeth ipsilateral to the tooth of interest (maximum score of 5). The hard tissue and soft tissue scores will be compared between two groups.

3. Duration and depth of anesthesia:

In addition to the initial onset, we would gather information about the depth of anesthesia (as tested by EPT and cold tests) at 15 min, 30 min and 1 hour after administration of anesthesia. This would help us identify the duration for which reliable pulpal anesthesia is maintained.

4. Anxiety in Adults:

Modified Dental Anxiety Scale (MDAS):

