5. What is the most important deciding factor for you to choose NASAL SPRAY ANESTHETIC for your dental needs?

Cost Fear and Anxiety

6. How much extra money would you be willing pay for the NASAL SPRAY ANESTHETIC?

\$20 \$50 Up to \$100 It is not worth paying extra

7. Did your experience with the NASAL SPRAY ANESTHETIC change your outlook towards receiving future dental care?

Nothing changed; Still scared of dental visits This appointment was better but am still concerned about my future visits This appointment definitely eased my apprehension of future dental visits

8. If you had known that there was an option of NASAL SPRAY ANESTHETIC, would you have sought dental care early?

Definitely No Maybe Definitely Yes

5. Survey after 24 hours:

A short one question about the side effects of local anesthetic will be asked to the patient in person or over phone at 24 hours.

Did you suffer any of the following side-effects after your dental visit?

- nasal drainage,
- nasal congestion,
- burning,
- pressure,
- sinus congestion,
- pain and soreness at the site of the anesthesia (scored from 1-10)
- Numbing or tingling in throat
- other (Specify)_____

Flow of research study visit in adults (>18 years):

Screening of EHR will be done to identify potential study participants on a routine clinical visit. During the study visit the study related procedures would be preformed in the following order:

1. Go over the study details, answer participant questions and obtain informed consent
2. Administer MDAS anxiety survey
3. Ask patient to rate pain (if present) in the Heft Parker Scale
4. Reveal allocation (Kovanaze or Articaine)
5. Take baseline BP and heart rate
6. Administer local anesthetic
7. Wait for patient to signal achievement of meaningful anesthesia (using stop watch)
8. Map the extent of soft tissue and hard tissue anesthesia in data collection form
9. Proceed with the intended procedure
10. Assign anesthetic **failure** if subject perceives pain after start of procedure. Record the failure in data collection form and proceed with rescue anesthetic to complete the procedure
11. Assign anesthetic **success** if local anesthesia was adequate to complete the intended procedure without need for rescue anesthetic. Record in data collection form
12. Administer MDAS survey for all participants
13. Administer satisfaction questionnaire to subjects in Kovanaze group only
14. Take end of appointment BP and heart rate

Primary Outcome Measure in Children:

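### The adult 24-hour survey scores soreness at an undefined site, so a rescued Kovanaze participant's score cannot be assigned to nose or gum; separately, nosebleed is not prompted

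*Combined protocol and SAP*

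**What the plan says.** The survey is item 5 under Secondary Outcome Measures in Adults: "A short one question about the side effects of local anesthetic will be asked to the patient in person or over phone at 24 hours". The stem is "Did you suffer any of the following side-effects after your dental visit", followed by seven named effects and an open option, "other (Specify". Six of the seven carry no score. They cover drainage and congestion of the nose, congested sinuses, burning, pressure, and a numb or tingling throat. The seventh is the only graded one: "pain and soreness at the site of the anesthesia (scored from 1-10".

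The routes are set out elsewhere in the document. Under Intervention, Kovanaze is given "in the nostril on the same side as the tooth of interest". Under Control, articaine is "delivered in the periapex of the tooth of interest by labial/buccal infiltration". Under Primary Outcome Measure in Adults, a failure of anesthesia leads to "rescue anesthetic (0.7 ml of articaine deposited at the periapex of the tooth of interest) administered to complete the intended procedure".

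The Exclusion Criteria include "Five or more nosebleeds in the past month". Nosebleed does not appear among the effects named in the survey.

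The satisfaction questionnaire is limited to the Kovanaze group; the 24-hour survey carries no such limit. No analysis of the survey is described, and the children's outcomes contain no counterpart to it.

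**The concern.** There are two separate weaknesses in one instrument.

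The first is attribution. A soreness score is useful if one knows what was sore. The item leaves the site to the respondent, and the two routes act on different parts of the body. Where a participant has had both the spray and an injection, one number is recorded for two places. A high score could be nasal irritation, injection soreness or both, and nothing collected in the survey separates them.

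The second is completeness. The survey prompts for lesser-known and common nasal complaints alike, but leaves out the one nasal event that the eligibility criteria screen for. Events that must be volunteered tend to be reported less often than events that are read out, so the count of nosebleeds would be gathered on a weaker footing than the counts of the listed effects.

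At stake is the description of how adults tolerate the spray. A 24-hour answer cannot be reliably reconstructed once the contact has passed.

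**Working it through.** The plan gives no figure for this survey, so there is none to reproduce. The check is a comparison of sections, followed by simple arithmetic for scale.

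**Step 1. Which site does the graded item refer to?** Taking it to mean where the drug was delivered:

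| Adult participant | Delivery site(s) | Scores recorded |
|---|---|---|
| Articaine, no rescue | gum at the tooth | 1 |
| Articaine, rescued | gum at the tooth | 1 |
| Kovanaze, no rescue | nose | 1 |
| Kovanaze, rescued | nose and gum at the tooth | 1 |

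Only the last row has more sites than scores. The wording could also be taken to mean the area that went numb, in which case an unrescued Kovanaze participant might answer about the teeth. The survey does not rule this out, but how often it would happen cannot be judged from the documents.

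**Step 2. How many participants fall in the last row?**

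Inputs:
- 45 Kovanaze participants per population (Non-inferiority threshold and Sample size calculation).
- Two adult populations, Populations 2 and 3, so 2 × 45 = 90 adults given Kovanaze.
- Reported Kovanaze success of 83-90% (Background), assumed to carry over to these adults.

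Expected number rescued = 90 × (1 − success):
- at 90%: 90 × 0.10 = 9.0
- at 83%: 90 × 0.17 = 15.3

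Per adult population this is 45 × 0.10 = 4.5 to 45 × 0.17 = 7.7 (rounded). Each further fall of 10 percentage points in success would add 90 × 0.10 = 9 participants. Success could be lower in Population 2, who have symptomatic irreversible pulpitis, but the documents give no rate for that group.

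For comparison, at the 78-88% quoted for articaine, 90 × 0.12 = 10.8 to 90 × 0.22 = 19.8 adults in that arm would be rescued, but at the same site as their first injection. The two-site problem is therefore confined to the Kovanaze arm.

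**Step 3. Can it be repaired afterwards?** In part. Steps 10 and 11 of the adult visit flow record failure with rescue, or success without it, so the affected participants can be identified. Their single score still cannot be divided between nose and gum.

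**Step 4. Nosebleed.** The criterion excludes five or more episodes in the past month, so people with fewer remain eligible. Nosebleed is not among the seven named effects. It can be recorded only under the open option, and this is so in both arms. The documents give no nosebleed rate and no rate of volunteering, so no number of missed events can be calculated.

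**The case against.** The strongest reply is that a difference in site is not in itself a defect. The trial compares a nasal route with an injected one, and soreness where each drug was given is a sensible route-level measure. Likewise, injection soreness after a failed spray is a consequence of being assigned to the spray and belongs in an as-randomised summary. Both arguments stand. What they do not answer is that, for rescued Kovanaze participants, the source of the score is unknown.

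A reader might infer several stronger points, which the documents do not support:

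- **That the missing nosebleed item makes the arms unlike.** It is unprompted in both arms, so it affects completeness of capture, not the like-for-like nature of the comparison.
- **That the protocol declares nosebleed a risk of the spray.** The criterion concerns recent history and gives no reason. The inference is fair but remains an inference.
- **That a nosebleed cannot be recorded.** The open option allows it.
- **That rescue status is missing.** It is recorded at the visit.
- **That the comparison under Specific Aim 2 fails.** That aim evaluates Kovanaze and names no comparator. No between-arm test of this survey is described; a comparison is only implied by its place among the secondary outcomes and its use in both arms. The aim also draws on other graded measures, such as the anxiety scale given before and after treatment.

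**Conclusion.** The point holds as a limited weakness in a secondary tolerability measure for adults. As worded, the only graded item yields a score that cannot be assigned to nose or gum in Kovanaze participants who receive rescue: about 9 to 15 of 90, on the assumptions that planned enrolment is met and that the 83-90% success in the Background applies. More would be affected if success is lower. Independently of that, nosebleed is likely to be captured less completely than the prompted effects, to an extent the documents do not allow one to quantify. Neither weakness bears on the primary outcome, the sample size or the non-inferiority conclusion.

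**What to change.** 1. Replace the single soreness item with two, asked of every adult in both arms: soreness in the nose, and soreness in the gum or tooth area. Use a scale that includes zero for each, since one that starts at 1 has no value for no soreness.
2. Add nosebleed to the prompted list.
3. State how the survey will be reported: each item by arm as randomised and, using the rescue status already recorded at the visit, also among Kovanaze participants without rescue. The second summary selects on an event after randomisation, so it should be labelled descriptive and not used as a comparison between arms.

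The cost is two extra questions at an existing contact (one from splitting the soreness item, one for nosebleed) and one extra table. No new rescue data are needed.

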Eligible procedures: Procedures that would require local anesthesia include direct restorations (fillings), pulpotomy or pulpectomy (partial or complete removal of pulp) and placement of stainless steel crowns.

The standard of care in Department of Pediatric Dentistry is to administer nitrous before start of the treatment to alleviate patient anxiety. We will follow routine clinical protocol to titer the dose of nitrous oxide to individual patient needs.

Additionally, we hypothesize that the degree and depth of anesthesia would vary based on the initial disease state as well as the intended procedure. Accordingly, impact of the anesthesia will be analyzed at the completion of study using subgroup analysis.

Population 2: Symptomatic adults (>18 years) with symptomatic irreversible pulpitis

Location: Department of Endodontics, 2nd floor, Lyons Building

Eligible procedures:

Root canal treatment in teeth with significant decay but presenting with signs and symptoms of irreversible pulpitis (symptomatic)

Additional Inclusion Criteria:

- Tooth with a diagnosis of symptomatic irreversible pulpitis with or without periapical periodontitis
- Diagnosis is confirmed by history of spontaneous pain or prolonged (lingering) pain on application of cold or electronic pulp testing
- Tooth should have moderate to severe pain at the study onset (>54 on Heft Parker VAS scale)

Additional Exclusion criteria:

- Tooth with no response to cold / electronic pulp testing
- Tooth with periapical pathosis as seen in the radiograph
- Tooth with no vital coronal pulp tissue upon access

Population 3: Asymptomatic adults (>18 years) requiring restorations or crowns

Location: Department of General Practice, 2nd floor, Lyons/ Wood Building

Eligible procedures:

Direct and indirect restorations in teeth with significant decay but presenting with signs and symptoms of healthy pulp or reversible pulpitis

Additional Inclusion Criteria:

- Asymptomatic maxillary tooth with a diagnosis of primary or secondary dental caries extending more than 70% the thickness of dentin as seen in the radiograph

Additional Exclusion criteria:

- Tooth with no response to cold / electronic pulp testing
- Tooth with periapical pathosis as seen in the radiograph
- Endodontically treated tooth

Randomization

a. Sequence Generation:

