The biostatistician on the study team ([name]) will generate random sequence using a computer. The randomization will be in block of varying size (4 or 6) and the list will be provided to the following lead faculty who will serve as co-investigators as listed below:

Population 1: Pediatric Dentistry, [name]

Population 2: Endodontics, [name]

Population 3: General Practice, [name]

b. Allocation Concealment:

All random assignments will be placed in sequentially numbered opaque envelopes and will be handled by a staff in the respective department (not a part of the study team). If the participant is found to be eligible for the study, the resident/ student will inform the patient about the study. The team will answer all questions regarding the study and will request consent to participate in the study. After obtaining written patient consent, the department staff (not a member of the study team) will reveal the allocation.

Outcomes:

Patient important outcomes are considered including the primary outcome of completion of intended procedure without rescue anesthetic. This dichotomous outcome (success or failure of anesthesia) is linked to patients' rating of pain on a validated Heft-Parker visual analog scale. The emoji scale will be used for children. Group comparison between the articaine and Kovanaze formulations for anesthetic success will be analyzed by using Fisher's exact test.

Secondary outcomes include objective assessment of hard tissue and soft tissue anesthesia, anxiety scale (STAI-Y6 short form for children and MDAS scale for adults).

[figure not shown]
Adult participants who receive Kovanaze will also be asked to complete a survey to assess the impact of Kovanaze on patient confidence in seeking dental care.

Primary Outcome Measure in Adults:

Proportion of study participants in whom intended dental procedure could be successfully completed without the need for rescue anesthetic.

Heft Parker Scale: Each patient will rate his or her initial pain on a Heft Parker visual analogue scale, a 170-mm line with various descriptive terms. The subjects will be asked to place a mark on the scale where it best described their pain level both at the start and any time during the procedure. To interpret the data, the VAS is divided into the following four categories:

- a. No pain corresponded to 0 mm on the scale.

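### Step 10 of the adult visit flow fails and rescues a patient for any perceived pain, whereas the primary-outcome rule requires VAS above 54 mm

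*Combined protocol and SAP*

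**What the plan says.** The Outcomes section ties the endpoint to the pain scale: "This dichotomous outcome (success or failure of anesthesia) is linked to patients' rating of pain on a validated Heft-Parker visual analog scale". The adult rules are then given in four places.

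- **Primary Outcome Measure in Adults, scale categories:** "Mild pain was defined as greater than 0 mm and less than or equal to 54 mm".
- **Primary Outcome Measure in Adults, failure rule:** pain during the procedure is a failure at "VAS >54), the local anesthesia would be considered a failure and rescue anesthetic" is then given.
- **Secondary Outcome Measures in Adults, item 1 (onset):** "Treatment will proceed as long as the VAS rating is below 54mm. i.e. no to mild pain". The same paragraph fails a patient at a "score of 54 or higher), the event would be considered anesthetic failure".
- **Flow of research study visit in adults, step 10:** failure is assigned "if subject perceives pain after start of procedure. Record the failure in data collection form and proceed with rescue anesthetic".

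Step 10 gives no VAS value and does not refer back to the primary-outcome section. Step 10 of the children's flow has the same wording.

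**The concern.** Step 10 is the point at which the primary outcome is assigned and written on the data collection form. It contradicts the definition of that outcome for every patient whose pain during treatment is above 0 and at most 54 mm.

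The consequence goes beyond labelling. Step 10 also orders rescue, and any rescue is a failure by definition of the endpoint. A patient rescued for mild pain has received more articaine, so nobody can learn whether he or she would have finished without it.

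The plan also disagrees with itself at exactly 54 mm: the scale calls it mild and the primary rule does not fail it, but the onset paragraph does. This is a single point on a 170-mm line and is minor.

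**Working it through.** **1. The two rules side by side (adults, during the procedure)**

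| VAS | Primary-outcome rule | Onset paragraph | Step 10 as written |
|---|---|---|---|
| 0 mm | continue | continue | continue |
| 30 mm (mild) | continue | continue | failure and rescue |
| exactly 54 mm | continue (mild) | failure and rescue | failure and rescue |
| above 54 mm | failure and rescue | failure and rescue | failure and rescue |

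Step 11 (success if no rescue was needed) does not settle the conflict, because step 10 itself orders rescue for perceived pain.

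**2. Which rule was meant.** Population 2 must enter with pain: "Tooth should have moderate to severe pain at the study onset (>54 on Heft Parker VAS scale". Treatment can start once the "patient report significant pain relief (<54 in VAS scale" criterion is met. A patient who enters at 80 mm and falls to 30 mm is validly started. If that residual pain persists, a literal step 10 fails the patient as soon as treatment begins. The VAS rule is therefore the likely intent.

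**3. The plan's sample size.** Inputs from the sample size section: margin 0.25, one-sided alpha 0.05, power 83%, articaine success 78–88%. With equal true rates of 0.78 and unpooled variance:

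n = (1.645 + 0.954)² × 2 × 0.78 × 0.22 / 0.25² = 37.1, which rounds up to 38 per group.

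This matches the plan. Power at n = 38 is 83.8%. The match needs the lower end of the cited range: 0.83 gives 31 and 0.88 gives 23.

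**4. Illustration: equal point loss in both arms.** Assumptions: 45 per group; 78–88% is success under the VAS rule; a one-sided 95% Wald bound is compared with the margin (the plan names Fisher's exact test and states no bound); equal true rates. The 10, 20 and 30 points lost to mild-only pain are assumed, since the documents give no figure.

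Power = Φ(0.25 / √(2p(1−p)/45) − 1.645)

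| Points lost per arm | from 78% | from 88% |
|---|---|---|
| 0 | p = 0.78: 88.8% | p = 0.88: 97.7% |
| 10 | p = 0.68: 81.5% | p = 0.78: 88.8% |
| 20 | p = 0.58: 77.6% | p = 0.68: 81.5% |
| 30 | p = 0.48: 76.7% | p = 0.58: 77.6% |

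**5. Illustration: Kovanaze truly 25 points worse (0.58 v 0.83).** The chance of a false non-inferiority claim is Φ((0.25 − gap)/SE − 1.645).

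- Equal point loss (10, 20 or 30 points from each arm): the gap stays at 0.25, so the rate is Φ(−1.645) = 5.0% each time.
- Proportional loss (10%, 20% or 30% of VAS-rule successes in each arm): the gap becomes 0.225, 0.20 or 0.175, and the rate 8.2%, 12.4% or 17.8%.
- Mild-only share 0.83/0.58 = 1.43 times as large with Kovanaze as with articaine: the gap stays at 0.25 and the rate is again about 5%. Above that ratio the gap widens and the rate falls below 5%.

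The direction therefore depends on how mild pain is distributed between the arms, which the documents do not say.

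**The case against.** The best defence is that the visit flow is a checklist that relies on earlier definitions. Step 7 mentions meaningful anesthesia without its VAS criterion, and step 10 mentions rescue without its dose or site, so staff must consult the outcome sections anyway. The primary-outcome sentence itself speaks of pain, sensitivity or discomfort before giving the cut-off, so step 10 may simply abbreviate it. The statement that procedures follow the listed order governs sequence and does not redefine the endpoint. VAS marks during the procedure are already planned, so a rescue at or below 54 mm should be visible in the data.

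Most of this stands as evidence of intent, and the planned VAS marks do limit the damage. It does not remove a contradictory written rule at the step where the outcome is assigned, in a trial run across three departments. Seeing a premature rescue afterwards also does not show what would have happened without it.

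A reader might infer two stronger conclusions, and the documents support neither.

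- **That the error rate is inflated to 8–18%.** This comes only from assuming proportional loss. Equal point loss gives no inflation, and nothing in the plan favours one pattern over the other.
- **That open-label staff would apply the looser rule in one arm.** The arithmetic is possible: 37/45 in each arm gives a Wald bound of −13.3 points, and failing five Kovanaze patients for mild pain (32/45 v 37/45) gives −25.7, beyond the margin. But four such patients (33/45) give −23.2, which passes, and nothing in the plan suggests arm-specific use.

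**Conclusion.** The inconsistency is real and concerns the primary endpoint. Adult step 10 contradicts the VAS rule for mild pain, and the onset paragraph differs from the primary rule at exactly 54 mm. The VAS rule is the likely intent. Followed literally, step 10 would rescue and fail patients with mild pain, including Population 2 patients validly started with residual mild pain.

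The size and direction of the effect on the non-inferiority comparison are unknown. Under the assumptions in the working, equal point loss costs a modest amount of power (89–98% down to 82–89% at 10 points, and about 77–78% at 30 points) and leaves the false-claim rate near 5%. Other patterns could move that rate either way. The conflict itself rests on the text alone and on none of these figures.

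This is an internal inconsistency that should be fixed. It would be too strong to say that it invalidates the comparison or biases it in a known direction.

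**What to change.** - Reword adult step 10: assign failure and give rescue if VAS during the procedure is above 54 mm; any rescue given counts as failure.
- Use the same inequality in the onset paragraph: proceed at 54 mm or below, failure above 54 mm.
- Record the VAS at the time of any rescue.
- Report rescues given at 54 mm or below in a sensitivity analysis, counting them first as failures and then as successes, so that the VAS-rule result is bounded.
- Put the matching cut-off into the children's step 10 once the direction of the emoji scale is corrected. The children's outcome sections currently treat scores below 4 as painful in one place and as no to mild pain in another.

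The cost is a few wording edits, one recorded value and one extra analysis. No patients are added and the sample size does not change. The edits to step 10 need to be in place before patients are treated, because a rescue already given cannot be reversed.
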